11.2 Study Endpoints

11.2.1 Primary Endpoint

[figure not shown]
Primary safety measures will include the following:

[figure not shown]
- Treatment-emergent AEs and SAEs
- ECG recordings (Central Laboratory manual over-read), interpretation, and intervals
- Vital signs
- Serum Troponin I concentrations
- Laboratory abnormalities
- Physical examination abnormalities

11.2.2 *Secondary Endpoints*

The following are secondary endpoints:

- The human PK profile of MYK-491. The analysis includes at a minimum the following PK parameters. Additional PK parameters may be determined as appropriate.
 - C_{max} for each dose level
 - T_{max} for each dose level
 - AUC for each dose level dose
 - Apparent first-order terminal elimination half-life ($t_{1/2}$)
 - Mean residence time (MRT) for each dose level
 - Accumulation ratios determined (with the appropriate confidence intervals) for C_{max} and AUC_{0-t} (Part 2 only)
- SET as determined using TTE. The main parameters are the change from Baseline at each timepoint by treatment levels and the maximum change from Baseline.
- The following as assessed by TTE:
 - Change from Baseline in LSVV (derived from LVOT-VTI)
 - Change from Baseline in LVEF
 - Change from Baseline in LVFS
 - Change from Baseline in SET

11.3 Statistical Analysis

Before database lock, a statistical analysis plan (SAP) for clinical data and an analysis plan for PK will be prepared that will contain full details of all planned analyses. The analyses presented here represent an outline of the intended methodology.

11.3.1 Analysis Populations

Three analysis populations are defined in this study, the Safety population, the PK Analysis population, and the PD Analysis population.

The Safety population is defined as patients who are randomized and receive any amount of study medication (MYK-491 or placebo), including patients who prematurely withdraw from the study. Except as noted, all safety analyses, including demographic and Baseline characteristics, will be performed based on the Safety population.

The PK Analysis population is defined as patients who are randomized and receive any amount of MYK-491, have detectable plasma concentration data, and have no major or critical protocol deviations related to IMP (eg, incomplete ingestion of the drug, vomiting up to 8 hours after drug administration). During the placebo dosing period, a single plasma sample will be evaluated near the predicted T_{max} of MYK-491 to confirm lack of circulating MYK-491 and will not be included in the PK Analysis population.

The PD Analysis population is defined as patients who are randomized and receive any amount of study medication (MYK-491 or placebo), have any interpretable PD data, and have no critical or major protocol deviations related to IMP (eg, incomplete ingestion of the drug, vomiting up to 8 hours after drug administration). The PD analyses will be performed based on the PD Analysis population.

The PK/PD analysis will be performed based on MYK-491-treated patients that are in both the PK Analysis population and the PD Analysis population and/or Safety population depending on which parameters are to be included in the PK/PD analysis.

11.3.2 *General Considerations*

Clinical data will be summarized by treatment group. Descriptive summary statistics for continuous variables will include the number of patients, mean, standard deviation (SD), median, minimum, and maximum. Categorical variables will be summarized using counts and percentages.

11.3.3 *Patient Disposition*

The number and percentage of patients who complete or discontinue the study, as well as reasons for early discontinuation, will be presented.

11.3.4 *Demographics and Baseline Characteristics*

Demographic and Baseline characteristics will be summarized descriptively.

11.3.5 *Pharmacokinetic Analyses*

Plasma [REDACTED] concentration data for MYK-491 will be summarized using descriptive statistics, including mean or geometric mean as appropriate, SD, median, minimum, and maximum values and CV%. PK parameters will include (but are not limited to) C_{max} , T_{max} , AUC, apparent first-order terminal elimination rate constant (λ_z), and MRT. In addition, the accumulation ratios will be calculated with C_{max} and AUC_{0-t} (t = dose interval or τ) after dose on Day 9 (at steady-state) and Day 3 (1st dose). Additionally, the apparent terminal-phase elimination half-life ($t_{1/2z}$) will be calculated.

[REDACTED]

[REDACTED]

11.3.6 *Pharmacodynamic Analyses*

TTE data for LVEF, SET, LVFS, LHSV will be analyzed using descriptive statistics. No inferential analysis will be performed. Observations by timepoint and change from Baseline (either absolute or percent relative change) at each timepoint will be summarized by treatment period (Part 1) and treatment group (Part 2). Change from Baseline will be analyzed with attention to the relationship to time postdose, dose level, and comparison with placebo. For SAD Cohorts, placebo-adjusted change from Baseline will be calculated for each subject at each postbaseline timepoint and then summarized at each dose level. In addition, for SAD and MAD Cohorts, least square means of placebo-adjusted change from Baseline for the key PD parameters (LVEF, LVFS, LHSV, SET) at each postbaseline time point at each dose level may be estimated using mixed model.

The relationship between the TTE endpoints and MYK-491 plasma concentration will be assessed using linear or nonlinear correlations.

11.3.7 *Safety Analyses*

All safety analyses except SET as determined by TTE will be performed on the Safety Analysis population. Analyses of SET as determined by TTE will be performed on the PD Analysis population.

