The PK population will include all patients who receive MYK-491, have detectable plasma concentration data, and have no major or critical protocol deviations related to IMP (eg, incomplete ingestion of the drug, vomiting up to 8 hours after drug administration). In addition, a single plasma sample near the predicted time of maximum observed plasma concentration (T_{max}) of MYK-491 will be evaluated to confirm lack of circulating MYK-491 for the dosing period(s) when the patients received placebo.

Plasma concentration [REDACTED] data for MYK-491 will be summarized using descriptive statistics, including mean or geometric mean, as appropriate, SD, median, minimum and maximum values, and coefficient of variation (CV%). Other PK parameters include (but are not limited to) maximum observed plasma drug concentration (C_{max}), T_{max} , area under the plasma concentration-time curve over the dosing interval (AUC_{0-t}), AUC_{0-12} , AUC_{0-24} , AUC_{0-inf} after the single dose on Day 1 in Part 1 or Days 3 and 9 in Part 2 (in appropriate patients), trough concentration (C_{trough}), apparent first-order terminal elimination rate constant (λ_z) (on Day 1 in Part 1 and Day 9 in Part 2 only), and mean residence time (MRT). PK parameters at steady-state will be compared to those observed after the first dose in this study, and the accumulation ratios determined (with the appropriate confidence intervals) based on C_{max} and AUC_{0-t} after a single dose and at steady-state as well as λ_z . Additionally, the apparent terminal-phase elimination half-life ($t_{1/2z}$) will be calculated after each dosing day in Part 1 and on Day 7 in appropriate patients. [REDACTED]

[REDACTED]

Pharmacodynamic Analyses:

The PD Analysis population will include patients who have any interpretable TTE data. TTE data for LVSV (derived from LVOT-VTI), LVEF, LVFS, and SET will be analyzed using descriptive statistics. Observations by timepoint and change from Baseline (predose in that dosing period) for each timepoint will be summarized by treatment arms. Change from Baseline will be analyzed with attention to relationship to time postdose, dose level, and comparison with placebo. For SAD Cohorts, placebo-adjusted change from Baseline will be calculated for each subject at each postbaseline timepoint and then summarized at each dose level. In addition, for SAD and MAD Cohorts, least square means of placebo-adjusted change from Baseline for the key PD parameters (LVSV [derived from

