4 OVERALL STUDY DESIGN AND PLAN

4.1 Study Design

This is a two-part study. Part 1 will evaluate single-ascending doses of MYK-491 (SAD Cohorts) and Part 2 will evaluate multiple-ascending doses of MYK-491(MAD Cohorts).

Note: Part 2 (MAD portion) of the study is planned to start before Cohort 2 of Part 1 (SAD Cohort) is complete. If a patient at a site qualifies for enrollment in either Part 1 (SAD) or Part 2 (MAD), Part 2 will generally take priority; however, a patient may enroll in both, ie Part 1 (SAD) followed by Part 2 (MAD) or Part 2 (MAD) followed by Part 1 (SAD). In such cases, sites should consult with the monitoring team to discuss details.

4.1.1 *Part 1 Study Design*

Part 1 is a randomized, crossover, DB, placebo-controlled, two-cohort, sequential ascending (oral) single-dose study in ambulatory patients with heart failure. All patients will receive placebo and 2 or 3 active doses of MYK-491. Each patient will undergo sequential, single-dose treatment events separated by no fewer than 5 days and no more than 14 days. Patients in Cohort 1 may also return for a fourth dosing period (open label) after the SRC reviews available data and recommends the dose. Patients enrolled prior to the implementation of Amendment 1 may be offered the opportunity to return for the open-label period. Patients who return for this additional period must sign the amended informed consent form (ICF). Patients in Cohort 2 may participate in 2 to 4 dosing periods, based on SRC decision. Patients will be randomized to 1 of the different dosing sequences outlined in [Figure 1](#). Multiple patients can be dosed at the same time or during the same week depending on administrative issues, ie, capacity and scheduling.

For each dosing period, patients will be admitted to the clinical site on Day -1. Patients will be assessed for absence of exclusion criteria (eg, new lab abnormalities and/or conditions that indicate the patient is clinically unstable). They will receive MYK-491 or placebo in the morning of Day 1 followed by serial PK and PD assessments, as well as serial safety assessments. Patients will be discharged on Day 3 (ie, ~48 hours following Day 1 dosing). An additional outpatient plasma PK sample will be taken on the morning of Day 4 at 72 hours postdose.

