Patients will be dosed twice daily (every 12 hours). Doses may occur ± 2 hours from scheduled dosing times as long as doses are separated by at least 10 hours and by no more than 14 hours. The exception to the twice daily dosing is on Day 9 (last dose of randomized DB study drug treatment). On Day 9, a single morning dose will be administered followed by 72 hours of PK and PD assessments.

Before each dosing event, all available safety data from the previous days will be reviewed (for non-confined patients, if a home health nurse is utilized, the nurse and site will be in daily communication to ensure safety). Dosing of DB treatment will take place at approximately the same time each day.

[figure not shown]
A full PK profile and multiple TTEs and ECGs will be obtained on Days 3 and 9 (corresponding to first and last day of DB treatment respectively) before and after the morning dose.

Patients will return for a Follow-up visit 7 days following the last dose of study drug. In case of premature permanent treatment discontinuation, end-of-treatment visit (same assessments as Day 9) will be performed as close as possible to last DB dose (ie, as best as possible on day of last dose or next day). This visit should include (but is not limited to) the following assessments: TTE, PK, 12-lead ECG, safety labs, troponin and adverse events.

Note: Screening may continue during planned and unplanned SRC meetings. The protocol-specified Screening window may be extended to account for delays due to SRC meetings.

Recommendations by the SRC will include, but not be limited to: (a) evaluation of dose-modification and dose-stopping criteria; (b) doses to be given in specified cohorts; (c) size of specified cohorts; and (d) modification of the number and timing of PK and PD assessments (see [Section 4.4.1](#)).

Figure 1 Study Schema

BID, twice daily; MAD, multiple-ascending doses; PLBO, placebo; QD, once daily; R, randomization; SAD, single-ascending doses; SRC, Safety Review Committee; TBD, to be determined (Period D is optional, based on SRC evaluation).

NOTE: Additional Cohorts D and E, and possible additional cohorts, may be enrolled, eg to explore QD dosing or an alternative BID regimen.

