The bioanalyst assaying the PK samples will be unblinded so only the appropriate samples will be analyzed. On days in which the patients received placebo, only 1 sample obtained at about the time of the predicted maximum plasma concentration will be assayed to ensure that the patient received placebo.

7**STUDY TREATMENT**

IMP is defined as MYK-491 or placebo. In Part 1 (SAD), study patients will receive separate ascending doses of MYK-491 (2 to 3 doses) and a single dose of matching placebo.

In Part 2 (MAD), study patients will receive single-blind placebo BID for Days 1 and 2 and will then receive DB treatment (either placebo or MYK-491) for 7 days (Days 3 through 9). In Cohorts A, B, and C, on Day 9 patients will receive a single dose of placebo or MYK-491 in the morning for serial PK/PD assessments, while on Days 3 through 8 patients in these cohorts will receive placebo or MYK-491 BID.

In optional Cohorts D and E, and possible additional cohorts, patients may receive placebo or MYK-491 QD or BID dosing as determined by SRC.

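### Section 11.3.1 removes a whole patient from the PK and PD populations for one major or critical IMP deviation, which discards validly dosed periods and days, and its PD definition conflicts with the synopsis.

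*Combined protocol and SAP*

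**What the plan says.** Section 11.3.1 limits the PK population to those given MYK-491 who also "have detectable plasma concentration data, and have no major or critical protocol deviations related to IMP". It offers two examples of such a deviation: a dose not fully swallowed, and vomiting within 8 hours of dosing. The PD population is defined in the same way: patients who "have any interpretable PD data, and have no critical or major protocol deviations related to IMP", with the same two examples.

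The synopsis repeats the exclusion for PK. For PD it says only: "The PD Analysis population will include patients who have any interpretable TTE data". It attaches no deviation condition to that definition.

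Section 7 states that "IMP is defined as MYK-491 or placebo", so a faulty placebo dose also counts as an IMP deviation.

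On design, Section 4.1.1 says "Part 1 is a randomized, crossover, DB, placebo-controlled, two-cohort, sequential ascending (oral) single-dose study". The synopsis gives 3 to 4 dosing periods per patient in Cohort 1 and 2 to 4 in Cohort 2. For Part 2, Section 4.1.2 says "Patients will be dosed twice daily (every 12 hours", with a single morning dose on Day 9. Section 11.3.6 computes the Part 1 placebo-adjusted change within each subject. Section 11.3.7 places the systolic ejection time (SET) analyses under safety but runs them on the PD population.

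**The concern.** A patient-level exclusion suits a trial with one dose and one profile per patient. Here each patient supplies several separately dosed units of data. In Part 1, a dose vomited in one period says nothing against a period given at least 5 days earlier or later, yet the wording removes all of them. In Part 2, a dose vomited on Day 9 cannot alter the first-dose profile of Day 3 or any echo taken before it, yet those go too.

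At stake are the secondary objectives (PK and echo-based PD) in very small groups: as few as 4 patients in Cohort 1 and 6 active patients in a Part 2 cohort. The SET safety summaries follow the PD population and would lose the same patients. The Safety population, and with it the primary safety measures in Section 11.2.1, is untouched.

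**Working it through.** **Plan's own figure.** Part 2 cohorts have 8 patients randomized 3:1. 8 × 3/4 = 6 active and 8 × 1/4 = 2 placebo; 3 cohorts × 8 = 24. This reproduces Section 4.1.2 and the minimum of 24. No power calculation exists to reproduce.

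**Part 1, Cohort 1 at its minimum size.** Inputs: 4 patients (Section 11.1) and 3 periods of 175 mg, 350 mg and placebo (Section 4.4.1), so 12 patient-periods. Suppose one patient's 350 mg dose is vomited and graded major.
- Excluding the patient: 3 of 12 periods lost, 2 of them correctly dosed.
- Excluding the period: 1 of 12 lost.
- 175 mg placebo-adjusted change: n falls from 4 to 3 under the first rule and stays at 4 under the second. Standard error ratio: √(4/3) = 1.155.
- For patients with 2, 3 or 4 periods, the valid share discarded is 1/2, 2/3 or 3/4.

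**Part 2, Cohorts A to C, faulty Day 9 dose.** From Table 5, echoes scheduled from Day 1 up to the Day 9 predose number 1 (Day 1) + 2 (Day 2) + 2 (Day 3) + 1 (Day 4) + 1 (Day 7) + 1 (Day 9 predose) = 8. Those after the dose number 1 (Day 9, 7 h) + 1 (Day 10) + 1 (Day 11) = 3. The wording removes all 11, and the full Day 3 PK profile as well; the event can affect only 3 of the echoes.

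**Part 2, how many patients could be caught.** Double-blind doses: Days 3 to 8 twice daily = 6 × 2 = 12, plus 1 on Day 9 = 13. The per-dose rate p of disqualifying deviations is not in the documents. It is assumed here over a range, with doses treated as independent. Per patient the chance is 1 − (1 − p)^13; for at least one of 6 active patients it is 1 − (1 − p)^78, since 6 × 13 = 78.

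| Assumed p | Patient has at least one | At least one of 6 active lost |
|---|---|---|
| 0.2% | 2.6% | 14.5% |
| 0.5% | 6.3% | 32.4% |
| 1% | 12.2% | 54.3% |
| 2% | 23.1% | 79.3% |

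Losing 1 of 6 raises the standard error of a mean by √(6/5) = 1.095, about 10%. A once-daily optional cohort has 7 double-blind doses, so its figures are lower (6.8% per patient at 1%). The 4 run-in placebo doses are also IMP by definition but are left out of this count.

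**The two PD definitions.** A patient with readable echoes and one major IMP deviation is in the PD population under the synopsis and out of it under Section 11.3.1. Both cannot be applied.

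**The case against.** Several points on the other side have weight.

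- **Only major or critical deviations count.** This stands as a limit. A reader might infer that any vomited dose removes the patient, but the text gives no grading rule, and one vomited evening dose among 13 might be graded lower. Still, vomiting and incomplete ingestion are the plan's own examples of what disqualifies.
- **The synopsis carries no PD exclusion.** Correct. The PD half of this point therefore rests on Section 11.3.1, and the conflict needs resolving in its own right. The PK exclusion appears in both places.
- **Section 11.3 calls itself an outline and defers detail** to an SAP and a PK analysis plan. Those plans are not in the text provided, so they may contain a period-level rule. What is written is nonetheless a stated patient-level rule, not an open question.
- **A period-level reading is possible.** Section 11.3.1 keeps the placebo-period plasma sample out of the PK population while the patient stays in, and Section 11.3.6 summarizes Part 1 by treatment period. Neither sentence addresses deviations.
- **Replacement and supervised dosing soften the loss.** Section 5.3.3 allows replacement at the sponsor's discretion, for at most 2 patients per cohort; Section 13.2.7 allows it when a deviation leaves inadequate data; Section 7.3 has staff verify ingestion. These lower the frequency and restore numbers, but they do not recover the valid data already collected.
- **Some data are lost under any rule.** If the faulty Part 1 dose is the placebo, the within-patient adjustment goes anyway. A fault shortly before Day 9 can spoil the steady-state profile.

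**Conclusion.** The point holds on the wording of Section 11.3.1. One major or critical IMP deviation removes the patient's correctly dosed periods in Part 1, and the unaffected Day 3 profile and earlier echoes in Part 2. The Part 1 cost is exact for the example given: 3 periods lost instead of 1, and a 175 mg standard error about 15% larger before any replacement. The Part 2 percentages are conditional on an assumed rate and on independence between doses, and they apply only to the twice-daily 13-dose cohorts; they are not a forecast.

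A reader might also infer that the rule selects better tolerators at every dose level. The documents do not support that. Loss of a patient's lower-dose and placebo data can arise only in the Part 1 crossover, since Part 2 is parallel-group. No dose-related vomiting is reported in the visible text, and the healthy-volunteer summary in Section 1.2 describes good tolerance at all doses. Such selection is possible in Part 1, but not shown.

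The study is descriptive, so no test or error rate is at risk. The loss is one of precision and usable data in small groups, plus an unresolved definition of the PD population that also governs the SET safety summaries.

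**What to change.** In Section 11.3.1, keep the patient in the population and define exclusion on the data.

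- **Part 1:** exclude only the dosing period with the major or critical IMP deviation. If that is the placebo period, drop the within-patient placebo adjustment but keep active-dose PK and unadjusted change from Baseline.
- **Part 2:** keep everything before the deviation and exclude only profiles or timepoints it can affect. Accumulation ratios still require a valid Day 3 and a valid Day 9 profile.
- **Timing:** have staff blinded to treatment decide exclusions before each cohort is unblinded. Section 6.2 lets cohorts be locked and unblinded separately, and designated sponsor statisticians, programmers and pharmacologists are already unblinded.
- **Consistency:** make the synopsis PD definition match Section 11.3.1.

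The cost is protocol and SAP wording. Some patients will contribute incomplete data, so n will vary by period and timepoint and should be shown. The by-timepoint summaries can accommodate this, as can the mixed model, which the plan makes optional.

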**Safety Assessments:**

Serum troponin and ECGs will be obtained as part of the Screening visit, before and/or after dosing on selected days. Refer to Schedule of Events for timing.

Safety assessments include medical history, physical examinations, SET as determined by TTE, 12-lead ECGs, continuous ECG monitoring by (a) telemetry, (b) Holter monitor recording or (c) equivalent technology, vital signs, observed and patient-reported AEs, serum troponin concentrations, and safety laboratory tests. Any abnormal findings judged by the investigator to be clinically relevant will be recorded as AEs.

Suspected ischemic events, new or worsening episodes of ventricular arrhythmias and troponin elevations will be sent for review by a Central Safety Adjudication Committee (see [Section 4.5](#)).

Statistical Analyses:**General Considerations:**

Clinical data will be analyzed separately for the SAD and MAD parts of the study. In Part 1, the placebo dosing periods will be pooled across cohorts to form a placebo group. Placebo subjects from all MAD Cohorts will be pooled to form one combined placebo group for analyses. No formal statistical hypothesis testing will be performed. Descriptive summary statistics for continuous variables will include the number of participants, mean, standard deviation (SD), median, 1st and 3rd quartiles, minimum, and maximum. Categorical variables will be summarized using counts and percentages. The 95% confidence intervals may be presented as well.

Safety Analyses:

SET, as determined by TTE, will be assessed using summary statistics. Observations and change from Baseline will be summarized by treatment at each timepoint and the

maximum change from Baseline will be determined for each patient. [REDACTED]

[REDACTED]

[REDACTED]

The number of patients with abnormal and/or rising troponin levels (taking into account potential troponin elevation at Baseline) will be determined.

Continuous ECG recordings by telemetry or Holter monitor (or equivalent) will be used to assess the nature, frequency, and severity of any ventricular arrhythmias or other significant cardiac rhythm abnormalities.

AEs, ECGs, vital signs, and laboratory values will be analyzed using descriptive statistics.

Pharmacokinetic Analyses:

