9.4 Safety Assessments

Safety will be assessed throughout the study as indicated in [Appendix 1](#) and [Appendix 2](#). Safety assessments include medical history, physical examinations, SET as determined by TTE, 12-lead ECGs, ECG telemetry (in confined patients), Holter ECG (in Part 2), vital signs, observed and patient-reported AEs, serum troponin concentrations, and safety laboratory tests. [REDACTED]

The actual timing of the assessment of ECGs, TTEs, and vital signs may be modified or up to an additional 2 sets of observations or samples per treatment period may be requested by the SRC after review of the data from previous treatment periods.

Any abnormal findings judged by the investigator to be clinically important will be recorded as an AE.

9.4.1 *Medical History*

A complete medical history will be recorded at the Screening visit, which will include evaluation (past or present) of the cardiovascular and heart failure medical history as well as the following: general, head and neck, eyes, ears, nose, throat, chest/respiratory, gastrointestinal/liver, gynecological/urogenital, musculoskeletal/extremities, skin, neurological/psychiatric, endocrine/metabolic, hematologic/lymphatic, allergies/drug sensitivities, past surgeries, substance abuse, or any other diseases or disorders as well as participation in clinical studies (study medication and/or device or other therapy). The medical history will be updated at admission if needed.

9.4.2 *Vital Signs*

Vital signs are to be assessed throughout the study as indicated in [Appendix 1](#) and [Appendix 2](#). The actual timing of the vital sign measurements may be modified and/or additional sets per treatment period may be requested by the SRC. Clinically significant abnormal values will be flagged. On days with multiple vital sign assessments, temperature needs to be assessed once, unless clinically indicated.

[figure not shown]
9.4.3 *Physical Examination*

Height (cm) will be measured at Screening and body weight (kg) will be measured at Screening and admission (first dosing period only in Part 1 [SAD]) BMI (kg/m²) will be calculated. Patients will be required to remove their shoes and wear indoor clothing as specified by the clinical site.

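### The SET safety summary is run on the PD Analysis population, so as written it can omit dosed patients who have readable echocardiograms

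*Combined protocol and SAP*

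**What the plan says.** SET measured by transthoracic echocardiography (TTE) has two roles in this protocol. Section 9.4 lists it as a safety measure: "Safety assessments include medical history, physical examinations, SET as determined by TTE, 12-lead ECGs". Section 11.2.2 lists it as a secondary endpoint; it is not among the primary safety measures in Section 11.2.1. A rise of more than 75 ms on two consecutive site-read TTEs suspends dosing in Part 1 (Section 4.2.1) and leads to dose modification in Part 2 (Section 4.2.3).

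The analysis sets are assigned as follows.

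- Section 11.3.1 puts every randomized patient who took any study drug into the Safety population, and adds: "Except as noted, all safety analyses, including demographic and Baseline characteristics, will be performed based on the Safety population".
- Section 11.3.7 states the exception: "All safety analyses except SET as determined by TTE will be performed on the Safety Analysis population". The next sentence gives the replacement set: "Analyses of SET as determined by TTE will be performed on the PD Analysis population".
- Section 11.3.1 requires members of the PD Analysis population to be randomized, dosed, to have readable PD data, and also to "have no critical or major protocol deviations related to IMP (eg, incomplete ingestion of the drug, vomiting up to 8 hours after drug administration".
- The synopsis, under Pharmacodynamic Analyses, says only: "The PD Analysis population will include patients who have any interpretable TTE data".
- The SET safety summary itself is descriptive: "SET, as determined by TTE, will be assessed using summary statistics". Section 11.3.7.1 adds changes by timepoint and a maximum change for each patient.

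Section 11.3 describes itself as an outline, to be followed before database lock by a SAP "that will contain full details of all planned analyses".

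**The concern.** Every other safety analysis keeps all dosed patients. For SET, a patient can be dropped because of something that happened after dosing. Incomplete ingestion is a dosing failure, but vomiting is a post-dose event that may be caused by the drug. Selecting patients for a safety table on such an event is what a Safety population is meant to avoid.

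The exclusion can also remove informative readings. In Part 2 the post-dose TTE is set at 7 hours, which Section 9.2.1 places near the expected peak effect. A patient who vomits just after that reading but within 8 hours has a usable near-peak SET value and still fits the example given for exclusion.

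The choice leaves the safety summary with little of its own. Section 11.3.6 already summarizes SET by timepoint and change from Baseline on the PD Analysis population. The safety summary repeats this on the same patients and adds only the maximum change. No visible planned SET summary covers all exposed patients with readable TTEs. At stake are what the end-of-study report commits to show for this measure and which patient count the table carries.

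**Working it through.** **1. Definitions side by side.**

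| Requirement | Safety population (11.3.1) | PD Analysis population (11.3.1) | PD Analysis population (synopsis) |
|---|---|---|---|
| Randomized and dosed | yes | yes | not stated |
| Readable TTE/PD data | no | yes | yes |
| No critical or major study-drug deviation | no | yes | not stated |

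Needing a readable TTE is unavoidable for an echocardiographic measure. The deviation row is the only one at issue. The synopsis does state that exclusion for the PK population, just before it defines the PD population, so its absence for PD is a real difference in wording.

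**2. What one patient-level exclusion removes.** The plan gives no exclusion rate, so an expected number cannot be computed. The fraction per excluded patient is 1/n, where n is the number on active drug at that dose.

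- Planned MAD cohort (8 patients, 3:1): n = 8 × 3/4 = 6; 1/6 = 16.7%.
- MAD cohort expanded to 24: n = 24 × 3/4 = 18; 1/18 = 5.6%.
- SAD Cohort 1 at its minimum of 4, all of whom receive each of the two planned active doses: 1/4 = 25%.
- SAD Cohort 1 at 8: 1/8 = 12.5%.

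**3. How this changes with the level of exclusion.** Section 11.3.1 defines the set in terms of patients. The plan does not say whether a deviation in one period or at one dose removes everything.

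- *By period.* In SAD the fraction is the same, but only for the affected period; the patient's other periods stay. MAD has a single randomized treatment period.
- *By timepoint, SAD.* Table 3 schedules post-dose TTEs at 3, 6, 9 and 24 hours. A patient who vomits at 7 hours could keep the 3- and 6-hour readings and lose only the later ones.
- *By dose or timepoint, MAD (BID cohorts).* Double-blind doses: two a day on Days 3 to 8 and one on Day 9, so 6 × 2 + 1 = 13. From the first double-blind dose, Table 5 schedules TTEs on Day 3 (7 h), Day 4 (7 h), Day 7 (predose), Day 9 (predose and 7 h), Day 10 and Day 11. The doses followed by a scheduled TTE before the next dose are Day 3 AM, Day 4 AM, Day 6 PM, Day 8 PM and Day 9 AM, which is 5 of 13. The other 13 − 5 = 8 doses have no TTE of their own, so a rule at this level could remove nothing.

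**The case against.** The strongest reply is that this is a deliberate and disclosed choice. Section 11.3.1 allows for exceptions and Section 11.3.7 states this one in two plain sentences. SET is a secondary endpoint and a named PD measure, so analysing it on the PD set is defensible. That disposes of any claim that Sections 11.3.1 and 11.3.7 contradict each other. It does not provide a SET safety summary on all exposed patients.

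Several other points stand.

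- Only deviations graded critical or major exclude. Nothing says that one vomited dose among 13 would be graded so.
- Staff verify ingestion of the whole dose (Section 7.3), which makes incomplete ingestion less likely but does not bear on later vomiting.
- Up to two patients per cohort may be replaced (Section 5.3.3). This can restore the analysed number, though not the omitted patient.
- Vomiting as an adverse event is still summarized on the Safety population (Section 11.3.7.2).
- The SAP promised in Section 11.3 is not in the supplied text, and redacted text follows the synopsis SET paragraph. An all-exposed SET table may therefore be planned where it cannot be seen.

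Four stronger readings are tempting and not supported. First, a reader might infer that SET safety monitoring misses patients. The dosing triggers use site readings, and neither they nor SRC review is tied to this analysis set. Second, a reader might infer that the summary will understate SET prolongation. The direction is unknown, because vomiting may mark poor tolerance or may mean less drug absorbed. Third, a reader might take the fractions in the working as holding under any exclusion rule. Step 3 shows that they do not. Fourth, a reader might treat the synopsis as a rival definition. It also leaves out randomization and dosing, so it is mostly an abbreviation of Section 11.3.1.

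**Conclusion.** The point holds as a minor one. As written, the descriptive SET safety summary can leave out exposed patients with readable TTEs because of a post-dose event, and the synopsis does not show that exclusion.

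The size is uncertain and may be nil. The 5.6% to 25% range is the loss per excluded patient. It assumes that at least one dosed patient on active drug has a deviation graded critical or major, and that exclusion is by patient (or, in SAD, by period for that period only). The 5-of-13 count assumes the BID schedule of Table 5, without TTEs that the SRC may add or move.

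No formal hypothesis test is planned (Section 11.1), so no error rate or power is affected. Data from all patients who receive study drug are kept (Section 5.3.3), so the fuller summary remains possible.

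**What to change.** Amend Section 11.3.7 so that the SET safety summary, including the maximum change, uses all Safety-population patients with an interpretable post-dose TTE, by treatment received. Keep the deviation-free PD Analysis population for the PD analyses in Section 11.3.6. Align the synopsis wording with Section 11.3.1. Carry both into the SAP and state there whether PD exclusions apply by patient, period or timepoint. Because Section 6.2 lets each cohort be locked and unblinded on its own, settle this before the next cohort lock.

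The cost is a few wording changes and one extra table. The downside is that some TTEs taken after partly absorbed doses stay in the safety summary, and the two SET tables will have different denominators, which a footnote should explain. No dose or clinical rule changes.
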